## **3. RESEARCH METHODS**

### **3.1. Study design**

Observational, non-interventional drug and multi-center study in which subjects will be administered as part of routine practice at Korean health care centers by accredited physicians. At least 3000 subjects should be enrolled in this study based on the Article 6 of “Basic Standards for the Re-examination of New Medicines” notified by MFDS. However, with additional 3 years of study period, at least 100 subjects who are being treated with Inlyta within the approved indication will be studied for total of 9 years according to the review result by the MFDS per Pfizer’s request to adjust the number of subjects. The study can be performed in Korean health care centers where INLYTA® is prescribed for advanced renal cell carcinoma (aRCC) after failure of one prior systemic therapy which is the indication for INLYTA® and where post-marketing study is allowed by institutions.

To achieve the target sample size, the study is being conducted in prospective study design and retrospective study design.

Patients to whom INLYTA® is first administered or patients who are already on INLYTA® during the study period should be enrolled in the study. Observation should be done from treatment initiation of INLYTA® for at least 28 calendar days. There are no visits or activities mandated by this study and routine observation will be done during INLYTA® treatment.

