### **3.9.2. Interim Analysis**

As required by MFDS regulations, the periodic report should be submitted to MFDS every 6 months for the first two years and then annual report should be submitted to MFDS for the third, fourth and fifth year. The final report for the date collected until August 21, 2018 should be submitted in the sixth year, by November 21, 2018. For the additional study period, periodic report should be submitted to MFDS every 6 months, and the final report of the entire study period should be submitted by November 21, 2021. Interim analysis will be performed in time for the report submission.

Analysis will be performed for safety group and efficacy group for patients who are prescribed with INLYTA® for the first time and for patients who are already on INLYTA® separately, and for all enrolled patients.

- Safety group: Subjects who have been administered INLYTA® at least once and evaluated with safety-related endpoints at least once.
- Efficacy group:ITT (Intent-to-treat) group - subjects to whom INLYTA® is administered INLYTA® at least once.

Detailed methodology for summary and statistical analyses of data collected in this study will be documented in a Statistical Analysis Plan (SAP), which will be dated, filed and maintained by the sponsor. The SAP may modify the plans outlined in the protocol; any major modifications of primary endpoint definitions or their analyses would be reflected in a protocol amendment.

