## 5. MANAGEMENT AND REPORTING OF ADVERSE EVENTS/ADVERSE REACTIONS

### 5.1. Requirements for the study

#### 5.1.1. REQUIREMENTS

The table below summarizes the requirements for recording safety events on the case report form and for reporting safety events on the non-interventional study (NIS) adverse event monitoring (AEM) Report Form to Pfizer Safety. These requirements are delineated for three types of events: (1) serious adverse events (SAEs); (2) non-serious AEs (as applicable); and (3) scenarios involving drug exposure, including exposure during pregnancy, exposure during breast feeding, medication error, overdose, misuse, extravasation, and occupational exposure. These events are defined in the section “Definitions of safety events”.

Safety event	Recorded on the case report form	Reported on the NIS AEM Report Form to Pfizer Safety within 24 hours of awareness
SAE	All	All
Non-serious AE	All	None
Scenarios involving exposure to a drug under study, including exposure during pregnancy, exposure during breast feeding, medication error, overdose, misuse, extravasation; lack of efficacy; and occupational exposure	All (regardless of whether associated with an AE), except occupational exposure	All (regardless of whether associated with an AE)

For each AE, the investigator must pursue and obtain information adequate both to determine the outcome of the adverse event and to assess whether it meets the criteria for classification as a SAE (see section "Serious Adverse Events" below).

Safety events listed in the table above must be reported to Pfizer within 24 hours of awareness of the event by the investigator **regardless of whether the event is determined by the investigator to be related to a drug under study**. In particular, if the SAE is fatal or

life-threatening, notification to Pfizer must be made immediately, irrespective of the extent of available event information. This timeframe also applies to additional new (follow-up) information on previously forwarded safety event reports. In the rare situation that the investigator does not become immediately aware of the occurrence of a safety event, the investigator must report the event within 24 hours after learning of it and document the time of his/her first awareness of the events.

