3.1. Safety Analysis Set

Safety analysis set will be included all subjects who have been administered INLYTA® at least once and evaluated with safety-related endpoints at least once.

The case below shall be excluded from the safety analysis set in the following order:

- 1) Subjects who have been already completed for INLYTA® prior to the contract date.
- 2) Subjects who have not been administered INLYTA®.
- 3) Subjects who have not met the inclusion/exclusion criterion.
- 4) Subjects who have not been evaluated for any safety-related endpoints.
- 5) Subjects who have any significant protocol violation.

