3.2. Efficacy Analysis Set

Efficacy analysis set will be included subjects to whom INLYTA® is administered INLYTA® at least once. Subjects who are excluded from the safety analysis set shall be excluded from the efficacy analysis set.

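### SAP 3.1 drops dosed, eligible, safety-evaluated patients for an undefined significant violation, and SAP 3.2 carries every safety exclusion into ORR, PFS and TTP, so no analysis on the protocol's ITT group is planned

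*SAP*

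**What the plan says.** Protocol 3.9.2 gives two definitions. The safety group is "Subjects who have been administered INLYTA® at least once and evaluated with safety-related endpoints at least once". The efficacy group is "Efficacy group:ITT (Intent-to-treat) group - subjects to whom INLYTA® is administered INLYTA® at least once". Neither contains an exclusion for protocol violations. The same section asks for separate results for first-time users and "patients who are already on INLYTA® separately, and for all enrolled patients".

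SAP 3.1 opens with the protocol's safety definition and then removes five classes in a fixed order: (1) treatment completed before the contract date, (2) never dosed, (3) eligibility criteria not met, (4) no safety evaluation, and (5) "Subjects who have any significant protocol violation".

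SAP 3.2 opens with the protocol's efficacy wording, "Efficacy analysis set will be included subjects to whom INLYTA® is administered INLYTA® at least once", and continues: "Subjects who are excluded from the safety analysis set shall be excluded from the efficacy analysis set". SAP 4.2 takes the ORR denominator from this set, and SAP 6.3 runs best overall response, ORR, PFS and TTP on it.

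For excluded patients who were dosed, SAP 3.5, SAP 6.2 item 6 and dummy Tables 36 and 37 give adverse events descriptively. SAP 6.4 repeats only items 1 to 4 of SAP 6.2 by sub-group.

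**The concern.** The study exists to describe adverse events in routine practice, and the regulator's minimum is 100 patients. An exclusion whose criterion is left open, with no statement of who applies it or when, leaves room for selection in the main adverse event figures. Through SAP 3.2 the same selection reaches every efficacy figure. The protocol promises an ITT efficacy group and the SAP plans no analysis on it. A reader who sees the ITT wording in the protocol, repeated in the first sentence of SAP 3.2, would take the reported ORR and PFS to cover all dosed patients, and they would not.

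**Working it through.** No figure in the plan is at issue, so the check is first a comparison of sets and then an illustration of size.

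**Step 1. Whom each exclusion removes.**

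| SAP 3.1 item | In protocol safety group? | In protocol efficacy group? |
|---|---|---|
| 1 Completed before contract | Yes, if dosed and evaluated | Yes, if dosed |
| 2 Not dosed | No | No |
| 3 Ineligible | Yes, if dosed and evaluated | Yes, if dosed |
| 4 No safety evaluation | No | Yes, if dosed |
| 5 Significant violation | Yes | Yes |

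The order is sequential, so a patient reaching item 5 has been dosed, is eligible and has a safety evaluation. For safety, item 4 agrees with the protocol. For efficacy, only item 2 does. Items 1 and 3 concern patients outside the intended study population and are easier to defend. Items 4 and 5 are not defensible on that ground. The SAP efficacy set is therefore the safety set under another name. It is smaller than the ITT group whenever any dosed patient falls under items 1, 3, 4 or 5.

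**Step 2. What planned output recovers.**
- Overall adverse event incidence: recoverable. Add the Table 37 numerator and denominator to those of Table 15. Table 36 gives counts by reason, so the eligible dosed group can be isolated.
- Relatedness: partly. Table 37 has an adverse drug reaction column; the finer causality categories are not shown.
- Serious events: not tabulated for excluded patients. Their number cannot exceed the Table 36 count of excluded patients with any adverse event.
- Severity, PFS and TTP: not produced for excluded patients.
- Overall ORR: can be bounded only, from Tables 26 and 36.
- New users and already-treated patients separately: not recoverable, because Tables 36 and 37 are not split.

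**Step 3. Size for ORR.** Let n be the number analysed, r the responders and k the eligible dosed patients excluded under items 4 and 5. The ORR in all n + k patients lies between r/(n + k), if no excluded patient responded, and (r + k)/(n + k), if all did. The documents do not give k, r or the sub-group sizes; the values below are assumptions. Intervals are Clopper-Pearson 95%.

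| k | Reported ORR | 95% CI | Bounds for all 100 |
|---|---|---|---|
| 3 | 19/97 = 19.6% | 12.2 to 28.9% | 19/100 to 22/100 = 19.0 to 22.0% |
| 5 | 19/95 = 20.0% | 12.5 to 29.5% | 19/100 to 24/100 = 19.0 to 24.0% |
| 10 | 18/90 = 20.0% | 12.3 to 29.8% | 18/100 to 28/100 = 18.0 to 28.0% |

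For a sub-group with 9 responders in 45 (20.0%, CI 9.6 to 34.6%), all k may have to be placed in that sub-group, because Table 36 does not say where they belong:
- k = 3: 9/48 to 12/48 = 18.8 to 25.0%
- k = 5: 9/50 to 14/50 = 18.0 to 28.0%
- k = 10: 9/55 to 19/55 = 16.4 to 34.5%

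All these bounds lie inside the matching sampling interval. If exclusion is unrelated to response, the expected ORR does not shift.

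**The case against.** **The SAP may change the plan.** Protocol 3.9 and 3.9.2 allow this, and ask for an amendment only for major changes to primary endpoint definitions or their analyses. No primary endpoint is named. A reader might infer a breach of the amendment rule; the documents do not support that. What stands is that the SAP narrows both sets without saying so.

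**The regulator may require it.** Protocol 3.12 says that the MFDS guideline governs the SAP, and that guideline is not among the documents. SAP 3.3 cites MFDS where it relies on it and SAP 3.1 does not, but this is weak evidence that item 5 is discretionary. The objection limits the remedy, which therefore needs a second branch. It does not supply the missing definition.

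**Excluded patients are reported anyway.** This is true for adverse events and drug reactions overall, so it would be wrong to say that these events are lost. It is not true for the other results listed in step 2.

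**Few violations are possible.** No visits are mandated and laboratory tests are optional, so k may be small. This is fair, and it is why no effect size is claimed.

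**Outcome-linked exclusion is speculative.** A reader might infer that early deaths would be excluded because "Observation should be done from treatment initiation of INLYTA® for at least 28 calendar days", or that patients with late-reported events would be, because "Safety events listed in the table above must be reported to Pfizer within 24 hours of awareness of the event by the investigator". Neither document says that short observation or late reporting is a significant violation, and reporting is the investigator's duty, not the patient's. These examples show why a definition is needed. They do not show bias.

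**Conclusion.** The point holds as a mismatch between the documents. The protocol's sets and the SAP's sets differ under a stated rule, the deciding term in item 5 is undefined, and no ITT efficacy analysis is planned. This rests on reading SAP 3.1 as sequential, which its wording states, and on the text supplied, in which no definition appears.

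The size is unknown and may be small. Under the assumed numbers, 3 to 10 exclusions per 100 leave the overall ORR uncertain by 3 to 10 percentage points (k/100), inside sampling error. A reader might conclude that the reported rates will be too favourable; the documents show no direction of bias, and no shift in PFS or TTP is claimed. It is a change that should be made because the remedy is cheap and removes a discretionary step, not because a distortion has been demonstrated.

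**What to change.** **SAP 3.1.** Delete item 5, keep these patients in the main safety tables, and repeat headline adverse event incidence without them as a sensitivity analysis.

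**SAP 3.2.** Replace the carry-over sentence so that items 4 and 5 remove nobody from ORR, PFS and TTP. If items 1 and 3 are kept as study-eligibility conditions, state them openly as a departure from the protocol's efficacy definition, since the resulting set is still not the literal ITT group.

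**If the MFDS guideline requires item 5.** Say so in SAP 3.1 and list the qualifying violations before database lock. Then also report adverse event and serious adverse event incidence, ORR, PFS and TTP, overall and for each sub-group, in all eligible, consented, dosed patients. No new consent wording is needed, because Protocol 3.2.2 and 3.5.4.2 and SAP 2.3.2 already keep patients who do not agree to use of their data out of the study.

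**Cost.** SAP wording and one extra set of outputs. The main tables will include a few patients with protocol departures, whose influence the sensitivity analysis will show for adverse event incidence.

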3.2. Efficacy Analysis Set

Efficacy analysis set will be included subjects to whom INLYTA® is administered INLYTA® at least once. Subjects who are excluded from the safety analysis set shall be excluded from the efficacy analysis set.

3.3. Special Patient Population

As required by MFDS guidelines, if any of the following special patient population is identified, sub-group analysis will be conducted for:

- Pediatric subjects (aged < 19 years)
- Geriatric subjects (aged ≥ 65 years)
- Subjects with renal impairment
- Subjects with hepatic impairment

3.4. Sub-Group Analysis Set

Sub-group analysis will be conducted for safety analysis set and efficacy analysis set for:

- Sub-group 1: Subjects who are first administered INLYTA® during the study period
- Sub-group 2: Subjects who has continued administration of INLYTA® since the time prior to the contract date

Statistical Analysis Plan for rPMS

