## 1. RATIONALE AND BACKGROUND

Renal cell carcinoma (RCC) accounts for 85% of kidney cancers, and is a collection of different types of tumors that arise from the renal epithelium. Renal cell carcinoma (RCC) is diagnosed in approximately 170,000 patients worldwide annually, resulting in 82,000 deaths.

Early stage disease does not typically produce significant clinical signs or symptoms, consequently 25-30% of newly diagnosed patients present with advanced (including locally invasive or advanced) or unresectable disease. The 5-year survival rate for advanced RCC is estimated to be ≤10%.

Most RCCs are highly vascularised tumors that over-express a number of growth factors, including VEGF (Vascular endothelial growth factor), PDGF (Platelet-derived growth factor) and fibroblast growth factor (FGF). The clear cell RCC subtype represents approximately 85% of the RCC population and frequently displays allelic loss on chromosome 3p, accompanied by mutational inactivation of the von Hippel-Lindau (VHL) tumor suppressor gene. VHL-associated RCC are known for their vascularity and these tumors produce high levels of vascular endothelial growth factor (VEGF). In addition, recent studies suggest that in sporadic clear cell RCC, increased expression of VEGF is closely correlated with neovascularization, which is a prerequisite of tumor growth and metastasis.

INLYTA®, a substituted indazole derivative, is an oral, potent, and selective inhibitor that blocks signal transmission via vascular endothelial growth factor receptor (VEGFR-1, -2 and -3) which is related to vascularization of tumors and tumor proliferation.

INLYTA® was first approved as new medicine on 22 Aug 2012. As required for any new medication approved by Ministry of Food and Drug Safety (MFDS), safety and efficacy information of new medication should be provided at minimum 3000 subjects administered in the setting of routine practice during the initial 6 years after the approval. However, based on MFDS's review upon Pfizer Korea's request, additional 3 years of study period has been granted to collect safety and efficacy information of minimum of 100 subjects.

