### **3.5. Study procedures**

#### **3.5.1. Study Duration**

As specified in the product license given by MFDS, this study was to be conducted for 6 years from the approval date of 22 Aug 2012 to 21 Aug 2018. On May 2018, MFDS has granted 3 additional years for the study, for total of 9 years for the study period.

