#### **3.5.4. Investigating Matters**

This means that the physician should enroll all subjects to whom INLYTA® is prescribed for the first time after contract is executed and who agree that Pfizer Korea and companies working with Pfizer Korea use his/her information by signing the 'data privacy statement'.

Data for patients who are currently on INLYTA® will be collected as much as possible following the categories for patients who are prescribed with INLYTA® for the first time.

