#### **3.5.4.1. Reporting of the study**

Final study report will include analysis for patients prescribed with INLYTA® for the first time, for patients who are already on INLYTA® at the time of enrollment, and for all enrolled patients.

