### 3.5.4.9. Safety

#### 3.5.4.9.1. Adverse Event

Every observed and reported adverse event, regardless of the causal relationship with the study drug, must be recorded on an adverse event section in case report forms. The query pattern of experience of adverse event to the subjects is as follow;

Patients who are prescribed with INLYTA® for the first time during the study period: “Have you had any health problem since last visit?”

Patients who are already on INLYTA® at the time of enrollment: all safety information will be collected from medical chart since the date of treatment initiation.

For adverse events repeating before and after administrating the study drug, record the date adverse event was first experienced and the date adverse event resolved. Background information on INLYTA® can be obtained from the current version of the local product document, which is the single reference safety document (SRSD) for information relating to INLYTA®.

Check either ‘yes’ or ‘no’ in adverse event section. If ‘yes’, record in detail.

- Adverse events: Record the name of adverse event. If possible, specify diagnosis, not individual symptoms. Record the name according to National Cancer Institute Common Terminology Criteria for Adverse Events (CTCAE) Version 5.0.
- Date of onset: Record the date of onset. Record approximate date if an actual date is unknown.
- Date of resolution: Record the date of resolution. Record approximate date if an actual date is unknown.
- Severity: Severity evaluation of adverse event must be done according to the NCI CTC grade.
  - The physician will use the following definitions of severity in accordance with the National Cancer Institute Common Terminology Criteria for Adverse Events (CTCAE) Version 5.0 to describe the maximum intensity of the adverse event:

Grade	Definition
Grade 1	Mild; asymptomatic or mild symptoms; clinical or diagnostic observations only; intervention not indicated.
Grade 2	Moderate; minimal, local or noninvasive intervention indicated; limiting age-appropriate instrumental ADL*.
Grade 3	Severe or medically significant but not immediately life-threatening; hospitalization or prolongation of hospitalization indicated; disabling; limiting self care ADL**.
Grade 4	Life-threatening consequences; urgent intervention indicated.
Grade 5	Death related to AE.

Activities of Daily Living (ADL)

\*Instrumental ADL refer to preparing meals, shopping for groceries or clothes, using the telephone, managing money, etc.

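### The SAP's two sub-group definitions use different date anchors and overlap, so Sub-group 1 as written takes in already-treated patients

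*SAP*

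**What the plan says.** SAP 3.4 sets out two analysis sub-groups. The first reads "Sub-group 1: Subjects who are first administered INLYTA® during the study period". The second is "Subjects who has continued administration of INLYTA® since the time prior to the contract date". The same wording recurs in SAP 6.1.6 and in the table footnotes. SAP 6.4 applies the split to most of the safety analyses and to all of the efficacy analyses.

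The study period is fixed in Protocol 3.5.1: "this study was to be conducted for 6 years from the approval date of 22 Aug 2012 to 21 Aug 2018", later extended to 9 years. Protocol 1 confirms that this is the first approval: "INLYTA® was first approved as new medicine on 22 Aug 2012".

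The protocol describes the same split in other terms:

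- Protocol 3.5.4 refers to patients prescribed the drug "for the first time after contract is executed", a contract anchor.
- Protocol 3.5.4.1 asks for a separate analysis "for patients who are already on INLYTA® at the time of enrollment", an enrolment anchor.
- Protocol 3.5.4.9.1 uses both the study period and enrolment. Patients first prescribed during the study period are questioned about health problems. For those already on drug at enrolment, "all safety information will be collected from medical chart since the date of treatment initiation".

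SAP 3.1 removes patients who finished INLYTA before the contract date, and SAP 3.2 carries that exclusion into the efficacy set. Neither document states that the sub-groups are mutually exclusive or which definition takes precedence.

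**The concern.** Two groups meant to partition the cohort should be cut at one date. Here one is cut at the start of the study period and the other at the site contract, and the first date is the day the drug was approved. Almost any patient treated with the marketed product was therefore first dosed in the study period, including those already on treatment when their site joined.

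This matters because the already-treated patients are selected. SAP 3.1 keeps a pre-contract starter only if treatment had not ended by the contract date. PFS and TTP are counted from first dose (SAP 4.2), and SAP 6.3 specifies a Kaplan-Meier analysis with no late-entry adjustment. If these patients count in Sub-group 1, its PFS curve includes time in which an early failure could not have been observed. Its response rate is computed on patients who stayed on treatment, and its adverse event incidence mixes prospective questioning with chart review. Protocol 3.5.4.1 and 3.9.2 and SAP 6.4 all require the new-user results separately, so this is a required reporting split.

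**Working it through.** **1. The plan's own figure.** Counted inclusively, 22 Aug 2012 to 21 Aug 2018 is 2191 days; 2191 / 365.25 = 6.00 years. To 21 Aug 2021 it is 3287 days; 3287 / 365.25 = 9.00 years. The stated 6 and 9 years reproduce.

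**2. Membership test.** Let s be the first-dose date and c the site contract date, for a patient on drug continuously from s until at least c where s is before c.

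- Sub-group 1: 22 Aug 2012 ≤ s ≤ 21 Aug 2021.
- Sub-group 2: s < c, and still on drug at c.

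Contract dates are not in the documents. Taking c = 15 Jun 2018 (the date of Amendment 6) purely as an illustration:

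| First dose | Sub-group 1 | Sub-group 2 |
|---|---|---|
| 21 Aug 2012 | no | yes |
| 1 Jan 2013 | yes | yes |
| 14 Jun 2018 | yes | yes |
| 15 Jun 2018 | yes | no |
| 1 Jan 2019 | yes | no |

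Only a first dose before approval puts a patient in Sub-group 2 alone. Whatever c is, every Sub-group 2 patient first dosed on or after approval also meets Sub-group 1.

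**3. Width of the overlap window**, (c − 22 Aug 2012) / 3287 days, for assumed contract dates:

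- 1 Dec 2012: 101 / 3287 = 3%
- 22 Aug 2015: 1095 / 3287 = 33%
- 15 Jun 2018: 2123 / 3287 = 65%
- 19 Feb 2020: 2737 / 3287 = 83%

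These are shares of calendar time, not of patients. Within the window, only patients still on drug at contract overlap.

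**4. Effect on the counts.** Take N = 100 (the required minimum), all first dosed after approval, with an assumed already-treated share q. Read literally, Sub-group 1 = 100 and Sub-group 2 = 100q. With one contract cut, Sub-group 1 = 100(1 − q) and Sub-group 2 = 100q.

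| q | Literal groups | Literal sum | One-cut groups | One-cut sum |
|---|---|---|---|---|
| 20% | 100 and 20 | 120 | 80 and 20 | 100 |
| 50% | 100 and 50 | 150 | 50 and 50 | 100 |
| 80% | 100 and 80 | 180 | 20 and 80 | 100 |

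**5. What the outputs need.** Table 7 shows the sub-groups as one classification with a single total. Tables 8 and 26 put the two sub-group columns beside a total. The listings in Tables 10, 12 and 14 carry one sub-group per subject. None of these can be filled consistently under the literal definitions.

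**6. Contract against enrolment.** A patient first dosed after the contract and enrolled some time later is a new user under Protocol 3.5.4 and belongs to Sub-group 1 alone under SAP 3.4. Under Protocol 3.5.4.1 the same patient is already on the drug. A contract cut removes the overlap in step 2 but not this disagreement.

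**The case against.** The best answer is that the intended reading is clear from context. SAP 6.4 contrasts first-time users with those already on the drug and analyses them separately. SAP 6.1.6 treats the split as one variable. Protocol 3.5.4 supplies the matching new-user rule, based on contract execution. On the literal reading Sub-group 1 is nearly the whole cohort, which nobody can have meant. The analysis is mainly descriptive, and no comparison between sub-groups is powered.

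This shows what was probably intended, but the SAP states a different rule and repeats it in every relevant footnote. A programmer who follows it gets the wrong Sub-group 1.

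The objection does limit the point in several ways:

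- A reader might infer that a new-user cohort cannot be isolated at all. The documents do not support that. Sub-group 2 has its own contract cut, patients who finished before contract are excluded, and drug start dates are recorded (Protocol 3.5.4.8). Sub-group 1 minus Sub-group 2 leaves those first dosed on or after the contract.
- A reader might take the calendar shares as the proportion of patients affected. They depend on assumed contract dates and do not measure patients.
- A reader might suppose that the protocol separates the groups because of selection or data collection. Protocol 3.5.4.1 and 3.9.2 give no reason; the argument about bias is this review's own.
- Moving both groups to the consent date is not needed to remove the overlap, and that date is not shown to be in the database. Protocol 3.5.4.2 describes a yes/no box completed once signature and date are obtained.

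**Conclusion.** The definitions are wrong as written. They are not mutually exclusive, and no precedence rule repairs them. Followed literally, Sub-group 1 contains every already-treated patient first dosed on or after approval. To call that essentially all of Sub-group 2 assumes little use before approval, which the documents do not quantify. The consequence is that patients who had to remain on drug until contract enter the new-user adverse event, ORR and PFS results.

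The number affected cannot be stated without the site contract dates and first-dose dates. It would be small if most sites contracted early and large if many joined late with patients already on treatment.

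The disagreement between the contract and enrolment anchors is a separate residual problem, also of unknown frequency. Because of it, a contract cut alone does not guarantee a cohort observed prospectively from first dose. Both should be settled before database lock, since allocation otherwise depends on how the rule is read.

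**What to change.** State in SAP 3.4 that the sub-groups are mutually exclusive and exhaustive, and cut both at one date:

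- Sub-group 1: first INLYTA dose on or after the site contract date, in line with Protocol 3.5.4.
- Sub-group 2: first INLYTA dose before the site contract date and still on the drug at that date. Say how a temporary interruption spanning the contract date is classed, so that nobody falls outside both groups.

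Derive the variable from the recorded drug start date and the site contract date. Use the same wording in SAP 6.1.6, SAP 6.4 and all table footnotes.

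Then reconcile it with Protocol 3.5.4.1 and 3.5.4.9.1. There are two acceptable routes. One is to adopt the enrolment date as the single anchor, if the sponsor confirms that the consent or enrolment date is in the database. The other is to keep the contract anchor, flag patients first dosed after contract but before enrolment, and repeat the Sub-group 1 results without them.

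The cost is a wording change, one derived variable and, on the second route, one repeated set of Sub-group 1 outputs. Sub-group 1 will be smaller than the literal text implies, and its confidence intervals correspondingly wider.
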